10.4 Analysis of secondary endpoints

- Number of flow-stop episodes will be analysed, in a generalized liner mixed model (GLMM), with subjects included as a random component. Evidence of effect will be concluded, if the lower 95% confidence limit of the risk ratio between comparator and investigational device, is greater than 1.
- Average residual volume post catheterisation will be presented with Descriptive statistics for a continuous variable (N, Mean, SD (standard deviation), Median, Min and Max.)
- Adverse events will be listed and/or summarized.

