5.3 Secondary Endpoints

- Number of flow-stop episodes derived from a catheterisation profile (catheterisation performed by a healthcare professional), (V2, V3) [number]
- Number of flow-stop episodes derived from a catheterisation profile (self-catheterisation), (V2, V3), [number]
- Residual volume at 1st flow-stop i.e., post catheterisation volume minus volume at 1st flow-stop, both derived from a catheterisation profile (self-catheterisation), (V2, V3), [mL]
- Average residual volume post catheterisation measured with the BladderScanner (triplicate measurements) (V2, V3) for both self-catheterisation and for HCP catheterisation, [mL]
- Number of Adverse events, [number]

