10.3 Analysis of the primary endpoint

Residual volume at first flow-stop, will be analysed in a linear mixed model (LMM) with subjects included as a random component. Evidence of superior effect will be concluded, if the 95% confidence interval of the difference between comparator and investigational device, does not include zero.

The model will include following fixed effects.

- Visit (visit 2 and 3 of catheterisation)
- Device (comparator and investigational device)

The primary endpoint will be evaluated with the null hypothesis being rejected at a 5% significance level (alpha 0.05).

Analysis of sensitivity

- The primary analysis will furthermore be analysed in the PP population, where subjects have received treatment as per protocol.

- Also, a Wilcoxon signed rank test will be applied the primary analysis, under the assumption of data not being normally distributed.

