10.8 Level of significance and power

A significance level of alpha 0.05 (2-sided) will be applied.

The power for concluding superiority of the investigational device is at least 90% or higher.

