10.9 Pass/fail criteria

To demonstrate superiority of the investigational device, the null hypothesis of the primary endpoint must be rejected, at a 5% significance (alpha 0.05).

11 Data management

Data management and the final statistical analyses of all measurements described in this protocol are carried out by the Clinical Strategies team, Coloplast A/S.

Data will be collected through an electronic data capturing (EDC) system on electronic Case Report Form (eCRF), a secure, internet-based case report form. This system will be used to record all subject information collected in the investigation for secure data tracking and centralised data monitoring ("remote monitoring") done by monitors, as defined in the monitoring section.

The EDC system used is Rave EDC, version 2022.3.0, delivered by Medidata Solutions Inc. The system is designed to be compliant with the FDA requirements of 21 CFR part 11. It is a validated data management system allowing only qualified and trained personnel to enter the system. The system has full audit trail and electronic signature.

The data management system has restricted role-based access control. The principal investigator or delegate an CRA must be trained in the system prior to getting access. The sponsor will be responsible for training the principal investigator or delegate, in completion of the eCRF. The training is web-based and must be completed before access to the investigation is granted. Training will be documented in the data management system. The data manager will also demonstrate the system on a virtual meeting. Only the principal investigator, or delegate, will be authorised to enter data in the eCRF.

The monitor, using his/her personal login information shall verify all critical data points against the source documents and issue electronic queries for the authorised clinical site personnel to respond, as defined in the monitoring section.

A critical quality control will be performed by the sponsor's data management team and queries issued where needed. Such queries must be resolved by the site personnel.

The principal investigator, using his/her personal login information, shall sign each eCRF before the database can be locked. This must be done after acceptance from the data management team.

Automated, real-time access to the data enable control on study compliance and safety assessments.

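### Section 10.4 allows a formal conclusion on two flow-stop endpoints at unadjusted 95% limits, with no testing order and no stated link to the primary test

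*Combined protocol and SAP*

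**What the plan says.** Section 5.3 names two flow-stop endpoints. One is "Number of flow-stop episodes derived from a catheterisation profile (catheterisation performed by a healthcare professional), (V2, V3) [number"; the other is "Number of flow-stop episodes derived from a catheterisation profile (self-catheterisation), (V2, V3), [number". Both are read at visits 2 and 3.

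Section 10.4 plans a generalised linear mixed model for the number of flow-stops, with a random subject term. Its decision rule reads: "Evidence of effect will be concluded, if the lower 95% confidence limit of the risk ratio between comparator and investigational device" is above 1. The rule is stated once, and the section does not say whether it means one model per catheterisation type or a joint model.

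Section 10.8 states: "A significance level of alpha 0.05 (2-sided) will be applied". It does not divide that level among endpoints. Section 10.9 ties the trial's success to one test: "To demonstrate superiority of the investigational device, the null hypothesis of the primary endpoint must be rejected". It says nothing about flow-stop conclusions. Sections 10.1 to 10.9 contain no testing order, no multiplicity adjustment and no condition that the primary test succeed before a secondary conclusion is drawn.

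Section 5.3 also lists residual volume at first flow-stop (RV1) for self-catheterisation as a secondary endpoint. Section 10.4 gives it no analysis.

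**The concern.** The flow-stop rule is a decision rule, not a descriptive summary. Applied to each endpoint in 5.3, it gives two chances to conclude an effect, each at the full level. A sponsor following the plan to the letter could conclude an effect from self-catheterisation alone when HCP flow-stops show none, or from either one when the primary RV1 test has failed.

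Flow-stops matter to the device's rationale. Section 5.6 connects them to mucosal suction and microtrauma, and section 21 reserves use of the data for regulatory and reimbursement purposes. The 5% level in 10.8 therefore protects each flow-stop test but not the pair, and the plan leaves open what may be concluded after a primary miss.

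**Working it through.** The plan states no error rate for the secondary conclusions, so there is no figure of its own to reproduce on the main point.

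**Inputs**
- Two-sided level 0.05 (10.8). The lower limit in 10.4 is taken as the lower end of a two-sided 95% interval, so each test has a 2.5% chance of a false favourable result. Nominal coverage of the model-based interval is assumed.
- Two flow-stop endpoints (5.3), tested separately (the natural reading).
- Correlation between the two test statistics, ρ: not given. Both come from the same subjects, visits and product (5.1), so a positive value is likely. The range 0 to 0.95 is an assumption.

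**Two flow-stop tests, both nulls true**

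P(at least one false favourable) = 0.025 + 0.025 − P(both statistics exceed 1.96).

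At independence this is 1 − 0.975² = 4.94%. For ρ > 0 the joint term comes from the bivariate normal distribution:

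| ρ (assumed) | P(both) | P(at least one) | Multiple of 2.5% |
|---|---|---|---|
| 0 | 0.06% | 4.94% | 1.98 |
| 0.3 | 0.24% | 4.76% | 1.91 |
| 0.5 | 0.46% | 4.54% | 1.82 |
| 0.7 | 0.83% | 4.17% | 1.67 |
| 0.8 | 1.10% | 3.90% | 1.56 |
| 0.9 | 1.48% | 3.52% | 1.41 |
| 0.95 | 1.77% | 3.23% | 1.29 |

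Whatever the dependence, the total cannot exceed 0.025 + 0.025 = 5%.

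**HCP first, self only if HCP succeeds**

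If the HCP null is true, any false claim requires a false HCP result first: at most 2.5%. If the HCP null is false, only the self-catheterisation claim can be false: again at most 2.5%. The 95% limits stay as they are.

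**What a gate on RV1 would cost**

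Table 3 gives 87.7% power for RV1 at a sample size of 60, so the primary misses with probability 1 − 0.877 = 12.3% even if its assumptions hold. That figure depends on what 60 means. With zero within-subject correlation, the SD of the paired difference is √(50² + 15²) = 52.2 mL.
- 60 per sequence: half-differences have SD 26.1, the standard error is 26.1 × √(2/60) = 4.77, and a two-sample t-test with 118 degrees of freedom gives 87.7%, as printed.
- 60 in total: the standard error is 52.2/√60 = 6.74, and a paired t-test gives 59.1%, a miss of about 41%.

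The sample-size table is a separate matter. Here it only sets the range for the cost of a gate.

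**The case against.** The strongest reply is that the trial's verdict is safe. Section 10.9 makes superiority depend on the primary endpoint alone, so the error rate of that claim stays at 5% two-sided. The plan also words its two rules differently: it speaks of superior effect in 10.3 and only of effect in 10.4. A reader may fairly take the flow-stop rule as supportive, and leaving supportive secondaries outside a familywise procedure is partly a design preference. This stands, and it limits the weight of the point. It does not say what a concluded effect means when RV1 has failed, or when the two flow-stop results disagree.

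A reader might infer three stronger things that the documents do not support.

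- *That the chance of a false flow-stop claim nearly doubles.* This holds only at or near independence. Measurements from the same subjects, visits and product are likely to be positively correlated, and at assumed correlations of 0.5 to 0.8 the multiple is about 1.8 to 1.6.
- *That the plan carries a 7.3% chance of some false favourable result over RV1 and both flow-stop tests.* The figure 1 − 0.975³ = 7.3% needs all three tests to be independent, yet HCP RV1 and HCP flow-stops are read from the same catheterisation profile. At a common correlation of 0.5 it is 6.3%.
- *That flow-stops are a declared main claim.* Section 5.6 explains why the endpoint was chosen. Section 3.1 names bladder emptying, safety and perception as objectives, not flow-stops.

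It is also fair that applying the rule twice is an inference, since a joint model is not ruled out, and that an order covering flow-stops alone leaves self-catheterisation RV1 undefined.

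**Conclusion.** The point holds as a limited gap in the secondary analysis. Section 10.4 permits a formal flow-stop conclusion at an unadjusted 95% limit, 5.3 supplies two endpoints to which it naturally applies, and nothing orders them or links them to the primary test. With both flow-stop nulls true, the chance of at least one false favourable conclusion is about 3.9% to 4.9%, against 2.5% for a single test, with a ceiling of 5%.

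This rests on three assumptions: two-sided 95% intervals with nominal coverage, separate models for the two catheterisation types, and a correlation between 0 and 0.8, which the documents do not state. A higher correlation would make the increase smaller. The superiority verdict in 10.9 is not affected. The change is a cheap improvement and not a condition for the validity of the primary result.

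**What to change.** 1. In 10.4, state that each catheterisation type has its own flow-stop model. Test HCP flow-stops first and self-catheterisation flow-stops only if HCP succeeds, each at two-sided 5%. This holds the flow-stop pair at 2.5% in the favourable direction.
2. In 10.4 and 10.9, state what follows from a primary miss: formal flow-stop conclusions are drawn only if the RV1 test succeeds, and otherwise the ratios and 95% intervals are reported as supportive, without a claim. Placed behind RV1 in this way, the whole sequence stays at or below 2.5% in the favourable direction.
3. State that self-catheterisation RV1 is descriptive, or give it an analysis and a place in the order.

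The cost is a few sentences, to be settled before database lock. The primary test loses no power and no subjects are added. The formal self-catheterisation claim is lost whenever HCP flow-stops miss. With the gate on RV1, every formal flow-stop claim is also lost when the primary misses: about 12% of the time on the plan's stated 87.7% power, and more if true power is lower (about 41% if 60 means subjects in total). The gate is therefore the costlier part, and the sponsor should choose it deliberately. Estimates and intervals are reported in every case.

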10.5 Analysis of exploratory endpoints

- Questions in the perception questionnaire will be summarised and listed.

10.6 Analysis of safety data

Adverse events will be listed and/or summarized. Device deficiencies and concomitant medications will be listed.

10.7 Sample size

Input for the sample size calculations i.e., means and standard deviations are based on three exploratory studies CP322, CP323 and CP324. The studies investigated earlier prototypes of the micro-hole catheter with identical or similar endpoints in populations of both IC users and healthy volunteers.

A sample size for the primary endpoint of residual urine at 1st flow-stop (RV1) is judged to be accommodated by 60 subjects with a power of ~ 90%, assuming a difference of 15 mL, a $sd_{comparator}$ of 50 mL and a sd_{active} of 15 mL (please see Table 3).

Table 3. Sample size calculation of Residual urine at 1st flow-stop in a cross-over design, solving for varying power and number of subjects, assuming no within subject correlation as a worst-case approach, using proc Power in SAS.

μ (sd) comparator	μ (sd) active	Alpha	Power	Sample size
25 (50)	10 (15)	0.05	71.9 %	40
25 (50)	10 (15)	0.05	81.2 %	50
25 (50)	10 (15)	0.05	87.7 %	60
25 (50)	10 (15)	0.05	92.2 %	70

Taken into consideration a discontinuation of 20%, the endpoint of RV1 is sufficiently supported by randomising at least 72 subjects.

If the number of subjects contributing to the primary analysis is less than 60 subjects, it must be carefully considered to include additional subjects (subjects replaced), to maintain sufficient power in the primary analysis.

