5.1 General

The investigation is a multi-centre, multi-national, randomised, controlled crossover study including 72 female IC users.

The total study duration for the individual subject will be approximately 4 weeks, consisting of four site visits and two 2-week test periods (T1 and T2) at home (+/- 3 days). Visits 0 and 1 can be performed on the same day. One self-catheterisation will be done at visit 1 with the first randomised product. For visit 2 and 3, two catheterisations (HCP and a self-catheterisation) will be performed in a hospital setting for bladder emptying assessment at each visit. At visit 2 the catheterisations will be done with the first randomised product, and at visit 3 the catheterisations will be done with the second randomised product. Test periods (at home) take place directly following visit 1 and 2. No data will be collected in the test periods at home. Visit 3 will terminate the study.

The study design and procedures are described below in figure 1.

[figure not shown]

Figure 1. Study design

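### Table 3 gives the power for twice the listed number of subjects: on the plan's own inputs, 60 subjects give about 59% power, not 87.7% or about 90%

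*Combined protocol and SAP*

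**What the plan says.** Section 10.7 states that residual volume at first flow-stop "is judged to be accommodated by 60 subjects with a power of ~ 90%, assuming a difference of 15 mL". The assumed means are 25 mL (comparator) and 10 mL (investigational device), with SDs of 50 and 15 mL. Table 3 is described as a "Sample size calculation of Residual urine at 1st flow-stop in a cross-over design", computed "assuming no within subject correlation as a worst-case approach, using proc Power in SAS". It lists power of 71.9%, 81.2%, 87.7% and 92.2% for sample sizes of 40, 50, 60 and 70.

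The same section then allows for 20% discontinuation, arrives at 72 randomised, and asks for replacement of subjects to be considered if fewer than 60 contribute to the primary analysis.

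Section 10.8 adds "A significance level of alpha 0.05 (2-sided) will be applied" and "The power for concluding superiority of the investigational device is at least 90% or higher".

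**The concern.** Every input needed to recompute Table 3 is printed, and the printed powers do not follow from them. They are much too high for a crossover in which each subject contributes one measurement per device. Sections 10.7 and 10.8 also disagree without any recalculation: 87.7% at 60 subjects is not at least 90%.

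The trial has a single pass/fail criterion, rejection of the primary null hypothesis (section 10.9). The 72 randomised and the replacement trigger of 60 both rest on this calculation. Ethics committees and authorities receive the plan with a stated miss probability of about 1 in 10. If the true figure is nearer 4 in 10, they are judging a different study, and a non-significant result would be wrongly read as coming from a well-powered one.

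**Working it through.** **Inputs**

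- Difference 15 mL (25 minus 10); SDs 50 and 15 mL; within-subject correlation ρ = 0 (section 10.7, Table 3).
- Alpha 0.05, two-sided (section 10.8).
- One pair per subject. The primary endpoint uses only the catheterisation by the health care professional (section 5.2), and section 5.1 has "At visit 2 the catheterisations will be done with the first randomised product, and at visit 3 the catheterisations will be done with the second" product. Residual volume from self-catheterisation is a secondary endpoint (section 5.3), so it does not supply a second pair.

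**Formulae**

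SD of the paired difference = sqrt(50² + 15² − 2ρ·50·15). At ρ = 0 this is sqrt(2725) = 52.2 mL.

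Noncentrality = 15·sqrt(n)/52.2, with n − 1 degrees of freedom. Power comes from the noncentral t distribution.

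For n = 60: 15 × 7.746/52.2 = 2.23, which gives power of 59.1%. Using n − 2 degrees of freedom, to allow for the visit effect in the section 10.3 model, also gives 59.1%.

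**Trying to reproduce Table 3**

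| Listed sample size | Table 3 | Power with n pairs | Power with 2n pairs |
|---|---|---|---|
| 40 | 71.9% | 42.6% | 71.9% |
| 50 | 81.2% | 51.3% | 81.2% |
| 60 | 87.7% | 59.1% | 87.7% |
| 70 | 92.2% | 65.9% | 92.2% |

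All four rows are recovered to the printed decimal when the number of pairs is doubled, and none is recovered with the listed number.

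**Other methods at n = 60, ρ = 0**

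- Normal approximation: 60.5%.
- Two-sample t test, 60 per group: 59.8% pooled, 59.3% Welch.
- Paired t test, one-sided alpha 0.05: 71.1%.
- Paired t test with the SD taken as 52.2/√2 = 36.9 mL: 87.2%. This is close but not exact, and it is the same factor of two, entered through the variance.

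**Size of the shortfall at ρ = 0**

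- If all 72 randomised subjects are evaluable: 67.2%.
- After the plan's 20% loss, 72 × 0.8 = 57.6, so 57 or 58 subjects: 56.8% or 57.6%.
- Evaluable subjects needed: 97 for 80% power, 130 for 90%.
- Difference detectable with 90% power at n = 60: about 22 mL rather than 15 mL.

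**Sensitivity to correlation**

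| ρ | SD of difference (mL) | Power, n = 60 | Power, n = 72 |
|---|---|---|---|
| 0 | 52.2 | 59.1% | 67.2% |
| 0.5 | 44.4 | 73.0% | 80.7% |
| 0.8 | 39.1 | 83.3% | 89.5% |
| 1 | 35.0 | 90.4% | 94.8% |

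At n = 60, power of 87.7% needs ρ of about 0.92, and 90% needs about 0.99.

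**The case against.** The strongest reply is that zero correlation is offered as a worst case. Repeated measurements in the same woman are plausibly positively correlated, so real power is probably above 59%. That is fair, and 59% should be read as conditional on the plan's inputs. It does not rescue the table, which is labelled as computed at zero correlation. Nor does it rescue section 10.8: with these SDs, 60 subjects reach 90% only if the correlation is almost perfect.

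Second, the mixed model in section 10.3 can use subjects with only one period, because the full analysis set requires only one recorded endpoint (section 10.2). As an illustration, suppose 60 subjects complete and 12 more give one observation each, split evenly between devices. Power is then about 65% by normal approximation, against 60.5% without them. This is a modest gain that leaves the conclusion unchanged.

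Third, an outcome with mean 25 and SD 50 that cannot be negative must be strongly skewed, so normal-theory power is approximate. That is true, and it limits how far any of these figures forecasts the trial's real power. The plan's own calculation has the same limit.

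Fourth, the cause is inferred. The exact match fits a per-sequence sample size read as a total, or observations counted as pairs; the SAS code is not in the documents. The mismatch does not depend on which explanation is right.

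Finally, the error affects neither the type I error nor the validity of a positive result. That stands.

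**Conclusion.** The concern holds. Under the plan's stated means, SDs, zero correlation and two-sided alpha of 0.05, with one pair per subject, power at 60 subjects is 59.1%. This is about 29 percentage points below Table 3 (87.7 − 59.1 = 28.6). The probability of missing a true 15 mL difference is about 41%. The table corresponds to twice the number of subjects that the plan uses as a total. The statement in section 10.8 is unsupported on the corrected figures and conflicts with Table 3 even as printed. If the true within-subject correlation is positive the shortfall is smaller, but at 60 subjects it disappears only at a correlation of about 0.92 (for 87.7%) or 0.99 (for 90%).

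**What to change.** - **Table 3 (section 10.7):** give 42.6%, 51.3%, 59.1% and 65.9% for 40, 50, 60 and 70 subjects in total. If the column is instead relabelled as per sequence, show totals of 80, 100, 120 and 140 and say plainly that the planned 60 evaluable and 72 randomised are well below the totals for the higher powers. Relabelling alone would not support 60 or 72.
- **Text of sections 10.7 and 10.8:** replace the statements of about 90% and at least 90% with about 59% at 60 evaluable subjects and 67% if all 72 are evaluable. State that the plan's 20% loss from 72 leaves about 57% to 58%.
- **Correlation:** if the three exploratory studies support a positive within-subject correlation, state the value, its source and the power that it gives, in place of zero.

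The cost is a correction to one table and two power statements, and a less favourable stated power. No extra enrolment is needed to make the statement correct. The correction does not raise the power; whether to enlarge the trial (about 130 evaluable for 90% at zero correlation) or to proceed at the lower power is then a decision for the sponsor on correct figures.

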4.6 Total number of devices intended for the clinical investigation

72 subjects will be included in the study. Subjects will be supplied with sufficient amount of test products to accommodate their usual catheterisation procedure for each test period. The investigational devices and comparators are packed in retail boxes with 30 products in each.

Example: The test period (home-use) is 2 weeks (14 days) and with an estimated usage of 6 catheters/day it equals 84 catheters, so subject will receive 3 retail boxes for home use (90 catheters) for each test period.

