6.3 Subject withdrawal criteria

The subject is allowed to withdraw from the investigation at any time for whatever reason without any consequences for their future treatment outside the clinical investigation. The principal investigator may withdraw a subject from the investigation at any time if they judge it to be the subject's interest.

The principal investigator must withdraw a subject from the investigation due to:

- Noncompliance with the CIP impacting the scientific integrity of the investigation.
- If a subject's safety and wellbeing is compromised by further participation.
- Subjects lost to follow-up. At least three documented attempts will be made to verify subjects lost to follow-up.

Randomized subjects that for some reason withdraw from the clinical investigation can be replaced.

Replacements should be discussed with Sponsor. Please also refer to section 10.7 Sample size for further information.

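### Randomising 72 does not cover the stated 20% discontinuation: 72 × 0.80 = 57.6, short of the 60 subjects the plan says it needs

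*Combined protocol and SAP*

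**What the plan says.** Section 10.7 (Sample size) says the RV1 endpoint "is judged to be accommodated by 60 subjects with a power of ~ 90%, assuming a difference of 15 mL". Table 3 in that section lists a power of 87.7% for 60 subjects. The allowance for loss follows: "Taken into consideration a discontinuation of 20%, the endpoint of RV1 is sufficiently supported by randomising at least 72 subjects".

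The next paragraph makes 60 a working floor: "If the number of subjects contributing to the primary analysis is less than 60 subjects, it must be carefully considered to include additional subjects". Section 6.3 adds a general permission: "Randomized subjects that for some reason withdraw from the clinical investigation can be replaced". It asks that replacements be discussed with the sponsor and refers back to section 10.7.

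Elsewhere the enrolment figure is a flat 72. Section 4.6 says "72 subjects will be included in the study", and the synopsis, section 5.1 and section 6 use the same number. No other derivation of 72 is given.

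**The concern.** The step from 60 to 72 looks like the common slip of adding 20% to the required number instead of dividing by the 80% expected to remain. If so, the plan's own discontinuation rate puts the expected number of subjects below the plan's own floor. The top-up discussion, written as a contingency, would then be the likely course.

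The sentence matters because it is the only justification for the number to be randomised. It also leaves no margin: Table 3 gives 87.7% at 60, while section 10.8 claims at least 90%.

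**Working it through.** **Inputs.** From section 10.7: 60 subjects needed, 20% discontinuation, 72 randomised, a difference of 15 mL, SDs of 50 mL (comparator) and 15 mL (investigational device), and zero within-subject correlation. From section 10.8: two-sided alpha of 0.05.

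**1. Reproducing the plan's figure.** 60 × (1 + 0.20) = 72, an exact match.

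**2. What 72 leaves after a 20% loss.** 72 × (1 − 0.20) = 57.6, which is 2.4 below 60.

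**3. What is needed to leave 60.** 60 / (1 − 0.20) = 75. Check: 75 × 0.80 = 60.

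**4. The loss that 72 can absorb.** (72 − 60) / 72 = 12/72 = 16.7%.

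**5. Chance of falling below 60.** Assume each subject independently has a 20% chance of discontinuing and that a subject who discontinues contributes nothing. The number remaining from N randomised is then Binomial(N, 0.80).

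| Randomised | Expected remaining | P(at least 60) | P(fewer than 60) |
|---|---|---|---|
| 72 | 57.6 | 0.295 | 0.705 |
| 75 | 60.0 | 0.569 | 0.431 |
| 80 | 64.0 | 0.893 | 0.107 |

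The row for 80 is included because section 5.8 randomises in blocks of 8, and 80 is the next whole number of blocks above 75.

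**6. Effect on power.** Table 3 is reproduced closely by an unequal-variance two-sample t-test with 2n observations per device. This gives 72.0%, 81.3%, 87.8% and 92.2% for n = 40, 50, 60 and 70, against the stated 71.9%, 81.2%, 87.7% and 92.2%. That this is how the table was made is an inference; the plan names only the SAS procedure. The standardised difference is 15 / √[(50² + 15²) / 2n]:

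- n = 60: 15 / √(2725/120) = 15 / 4.77 = 3.15, power 87.8%
- n = 58: 15 / √(2725/116) = 15 / 4.85 = 3.09, power 86.7%

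The loss is about 1.1 points. A paired t-test with one value per device per subject and zero correlation, where the SD of the difference is √2725 = 52.2 mL, gives 59.1% at 60 and 57.6% at 58, a loss of 1.5 points. (This 57.6% has no connection with the 57.6 subjects above.) Either way the dropout slip costs between one and two points. The gap between the paired figures and Table 3 is a separate and larger question, and the present point does not depend on it.

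**The case against.** Nobody disputes the arithmetic. The case on the other side is about weight.

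- **The effect is small.** Roughly one point of power is lost on the Table 3 basis, in a plan that already rounds 87.7% up to about 90%. The estimate, the type I error and the pass/fail rule in section 10.9 are untouched. This stands, and it limits how serious the point is.

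- **The plan has a safeguard.** The 72 is worded as a minimum, section 6.3 allows replacement, and section 10.7 asks for additional subjects to be considered below 60. If replacement is used, 57.6 is not the final count. This stands in part. Both provisions are discretionary, the rest of the plan works to a flat 72, and the sentence says that 72 has already taken the 20% into account.

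- **A subject who discontinues may still contribute.** Section 10.2 admits to the full analysis set anyone exposed to a device with one endpoint recorded, and the mixed model in section 10.3 can use a single visit. Of 72 × 0.20 = 14.4 expected discontinuations, 2.4 (one in six) leaving after a usable Visit 2 measurement would bring the count back to 60. This is fair, and it makes the 70% conditional on those who leave contributing nothing. However, section 10.7 itself sets discontinuation against the 60. A one-period subject also carries less information than one measured on both devices, and cannot enter the signed rank sensitivity analysis.

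**Conclusion.** The sentence is wrong as written. On the plan's own figures, 72 randomised with 20% discontinuation gives 57.6 subjects, not 60; 75 would be needed, and 72 covers 16.7%. These results need no assumption beyond section 10.7's own treatment of discontinuation as loss.

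The probability of about 70% of ending below 60 rests on two further assumptions: independent discontinuation, and no contribution from those who leave. The loss of about one point of power rests on the inferred basis of Table 3.

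The practical damage is modest, but the error is clear and the enrolment figure depends on it, so it should be corrected.

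**What to change.** Correct the sentence in section 10.7 in one of these ways:

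- **Keep 72 and restate the allowance:** 72 randomised subjects allow for discontinuation of up to 16.7% (12 subjects) while leaving 60.
- **Keep 72 and 20% and restate the yield:** about 58 subjects are expected in the primary analysis, with the power for that number (about 86.7% on the Table 3 basis). The threshold of 60 for considering additional subjects then needs rewording, because the expected count lies below it.
- **Keep both 20% and 60:** randomise 75 and update the figure in the synopsis and in sections 4.6, 5.1 and 6. Under the binomial assumption, 75 still leaves about a 43% chance of fewer than 60. Completing whole blocks of 8 would mean 80.

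The first two cost a text edit; the third costs three more subjects, or eight with whole blocks. In each case, section 10.7 should say whether a subject measured at Visit 2 only counts as contributing to the primary analysis, since the floor of 60 depends on it.
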